6.5.8 Handling of Withdrawals

In accordance with the Declaration of Helsinki, a patient has the right to withdraw from the study at any time, for any reason, without prejudice to any future medical care by the physician or the institution. The investigator and the sponsor also have the right to withdraw patients from the study in the event of serious adverse events, protocol departures (deviations, violations and exemptions), or other reasons. Should a patient (or the patient's legally authorized representative) decide to withdraw, all efforts will be made to collect and report the next visit observations, and the reasons for withdrawal, as thoroughly and timely as possible.

Withdrawals will be recorded, analyzed and reported to local ethical committee according to local regulations.

6.5.9 Patient lost to follow-up

If a patient does not show for a end-of-study visit and cannot be contacted to collect follow-up information, he/she will be counted as a 'missed visit'. Prior to counting the patient as a 'missed visit' the following will be performed:

- Repeated, documented attempts to contact the patient via all available means.
- Repeated, documented attempts to contact the patient's general practitioner or referring physician.
- If a visit cannot be arranged, obtain as much information as possible through all communication means with the patient and/or his/her treating physician.

If a patient is lost to follow-up, the methods used to attempt to contact the patient should be noted. At least three attempts should be made to contact the patient and/or his/her treating physician via all available routes, and a certified letter should be sent to the permanent address on file.

6.5.10 Enrollment Period

The anticipated enrollment rate is expected to be approximately 6-15 patients per month, depending on participating site. Enrollment period is expected to be up to six months long.

6.5.11 Procedures for Replacement of Subjects

No subject replacement is planned.

6.6 Study related Procedures

6.6.1 General

The potential candidates will be screened to assess whether they are appropriate candidates for inclusion in this study. Informed consent will be obtained prior to initiation of any of the following clinical procedures that are performed solely for the purpose of determining eligibility for research. Pregnancy test for female patients with childbearing potential will be performed. The patient medical history, migraine history and diagnosis will be recorded and verified, the use of concomitant medication will be recorded in designated case report forms. Eligible patients will receive a documented training, and upon its successful completion the investigational device will be handed to study participants for home use. As per the IFU, participants are instructed to activate the device at the onset of a migraine headache and manually adjust stimulation intensity to a level where it is perceivable but not painful. Participants are requested to refrain from use of rescue medications prior to and during the first two hours after treatment and, if could not comply with this, record their use in the cellular application. Via the smartphone application, each participant will be asked to rate his/her migraine pain level three times: (1) upon starting the treatment, (2) two hours after treatment, (3) 48 hours after first treatment corresponding to the current migraine attack, using Pain Grades Scale (0 - no pain, 1- mild pain, 2- moderate pain, 3 – severe pain). At the end of each treatment, participants will be asked to provide feedback using the application regarding the time elapsed from start of migraine attack to start of the treatment, their use of medication. In case of failure to provide feedback regarding pain level post-treatment, telephone follow-up will be performed by study investigator staff to solicit such feedback. Additional migraine symptoms will be self-reported using the application. Follow up phone calls will be scheduled to record change in medical condition, concomitant medication and migraine therapy. Unscheduled visits will be recorded and termination visit will be scheduled upon the completion of the study as defined by treatment of four qualifying attacks over the course of two months (whichever is achieved first). In the event of premature discontinuation an early discontinuation visit will be scheduled.

6.6.2 Visit and assessment schedule

The study requires two hospital visits: (1) for screening and device training and (2) end of study visit when the device is returned and end of study assessment is performed.

Screening and enrollment visit

During the screening visit, the following procedures will be performed:

- Review Inclusion /exclusion criteria and evaluate eligibility
- Informed consent signing
- Demographics and medical history review.
- History of migraines.

- Medication history and concomitant medication(s) review.
- Enrollment and randomization.
- Patients will receive the Narivio device and smart phone (per need)
- Patients will receive training on device and application operation and schedule of reporting.
- Completion of a questionnaire.
- Urine pregnancy test

End of study visit (3 months after enrollment)

During the screening visit, the following procedures will be performed:

- Participants will be asked about changes in concomitant medications and adverse events that have occurred during the study. Devices and smartphones will be returned.
- Completion of a questionnaire

6.6.3 Activities performed by sponsor representatives

It is the sponsor's responsibility to train the site staff and supply the devices in a timely manner.

It is also the sponsor's responsibility to communicate to other sites' representatives serious adverse events, device malfunctioning findings and other relevant information that may affect study operation.

6.7 Monitoring Plan

A detailed Monitoring Plan was developed for this study by the sponsor.

Monitoring functions will be performed in compliance with Good Clinical Practices guidelines per forth in ISO 14155 (2011). The major function of the clinical monitor is to observe and assess the quality of the clinical study and the data generated from it, and to ensure that patients' welfare is being kept.

Based on implementation of an EDC platform, remote monitoring will be possible and will be performed on a regular basis between monitoring visits. The Study Monitor/CRA will access the EDC to perform remote review of the data. Attention will be paid (but not limited to) to the following:

- Number of patients enrolled, per site.
- Timely data entry.
- Timely resolution of queries.
- AE/SAE and device deficiencies reporting in accordance with the protocol and according to the timelines, including adequate follow-up.
- Non-compliances documentation.
- Timely follow-up.
- Devices accountability

Due to utilization of integrated ePRO tools and EDC platform for data collection and management, electronic source data will be considered verified by nature of process validation and verification performed jointly by Theranica and the EDC vendor and documented separately.

A well planned and prepared Initiation Visit will take place to address and train the site on aspects of protocol adherence and data monitoring processes.

The following monitoring visits are planned in the course of the study:

- After the Site Initiation, a monitoring visit close to the first few (3-5) subjects' enrollment.
- After the study completion by first few patients
- After completion of study by all planned patients

In cases where the monitor notices that the PI is performing not according to the protocol or relevant regulation, the monitor should notify the sponsor by means of the monitoring report, email notification or a separate report if needed (i.e. Deviation Report Form). A follow-up letter to the PI should include the key findings. Site revisiting regarding GCP and protocol adherence should be done by the monitor in case of repetitive deviations.

7 STATISTICAL CONSIDERATIONS

7.1 *Study Design and Aim*

The study is designed as a prospective, randomized, double-blind, sham controlled multi-center clinical trial. The study aim is to demonstrate safety and effectiveness of Nerivio Migra electro stimulation device for treatment of migraine attacks with and without aura.

7.2 *Study Variables*

7.2.1 *Primary performance variable*

The primary performance endpoint, the proportion (%) of patients reporting freedom from pain (pain grade 0) 2 hours post treatment without rescue medications in at least 50% of treated attacks, will be measured in the form of a binary variable which will be assigned the value of "1" if the subject reports freedom from pain (pain grade 0) 2 hours post treatment without rescue medications in at least 50% of his/her treated attacks, and "0" otherwise.

7.2.2 *Secondary performance variables*

The secondary performance endpoints will all be expressed in the form of binary variables as in the representation of the primary performance variable.

7.2.3 *Exploratory performance variables*

The exploratory performance endpoint, the proportion (%) of patients reporting freedom from pain (pain grade 0) 48 hours post treatment without rescue medications in at least 50% of treated attacks, will be measured in the form of a binary variable which will be assigned the value of "1"

if the subject reports freedom from pain (pain grade 0) 48 hours post treatment without rescue medications in at least 50% of his/her treated attacks, and “0” otherwise.

Patient global impression of change is measured via a questionnaire.

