performed to record changes in medical condition, concomitant medication, migraine therapy and adverse effects. Unscheduled visits were recorded and termination visit were scheduled upon the completion of the study as defined by a maximal number of 20 complete treatment cycles but no longer than 6 months from enrollment. (whichever is fulfilled first). In the event of premature discontinuation an early discontinuation visit was scheduled. End of study interview was performed soliciting feedback regarding device usability, burden of treatment, use of migraine medications during the study period, as well as free comments.

Study Endpoints

- The primary efficacy endpoint of the study was the proportion of responders, where a responder is defined as subject with clinically significant decrease in pain score measured by Numeric Pain Rating Scale (NPS) of at least 50% 2 hours post treatment as compared to baseline in at least 50% of treatments.
- The second primary performance endpoint was relative pain reduction at 2 hours post treatment as compared to baseline.
- The primary safety endpoint was evidence of device related adverse effects.

Burden of treatment was assessed by mean scores of post-study questionnaire. Success was defined as superior performance of active treatments as compared to sham treatment. The protocol provided for enrollment of up to 100 patients.

Summary of Results

The pilot study was performed between June 2015 and March 2016. A total of 86 participants were provided with the Nervio Migra devices for use as part of this clinical study.

A summary of participants' demographic characteristics is presented in Table 2 below.

	Female	Male
N (%)	69 (80%)	17 (20%)
Age mean (min-max, STD)	45.2 (22-72, 11.7)	48.8 (26- 67, 11.7)
Migraine attacks per month, mean (STD)	5.1 (2.7)	5.34 (2.3)
Mean pain intensity during attack	8.9	8.6
Occurrence of aura	40 (58%)	11 (65%)

Table 2 – Pilot Study Population

Seventy-two participants successfully treated at least one migraine attack. The remainder of participants either did not treat their attacks per protocol, or failed to provide complete feedback. One participant was excluded from statistical analysis due to repeated use of rescue medications concurrently with the electro stimulation treatments. Complete reporting was obtained for 70% of activations for P200, P150, P100 programs, 58% of activations of P50 and 28% of placebo activations.

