7.4 Sample Size Estimation

The sample size for this study was calculated to test the above described null hypothesis with a chi-squared test, even though the final analysis may employ a regression model.

In the pilot study, the percentage of responders in the relevant treatment arm was 30%, while the percentage of responders in the sham group was 6%. The latter result is consistent with sham response rates referenced in IHS Guidelines for Migraine Trials. Sample size calculations are based on a more conservative estimate of the sham group response rate of 10%, then a sample size to detect a difference between treated and sham groups (of 20%) with 80% power at a 5% level of significance will result in a total of 124 evaluable subjects, with 62 subjects randomized to the treated arm and 62 to the sham arm. Allowing for a ~10% drop-out rate, a total of 136 (68 treated vs. 68 sham) subjects may be enrolled in the study.

Statistical considerations require availability of 124 evaluable subjects, i.e. with data available for analyses. The study recruitment will be monitored closely via the EDC system and, as soon as the evaluable data target is achieved, the Study Monitor will receive notification. If the number of subjects enrolled in the US is at least 50% of the accumulated population, recruitment will be stopped.

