7.8 Statistical Analyses

Amendments to the statistical analyses section will not require IRB approval, unless driven by protocol or study design change. In that case a standalone SAP will be prepared prior to data lock for each analysis milestone.

7.8.1 *General Considerations*

Statistical analyses will be performed using SAS® v9.4 (SAS Institute, Cary NC, USA).

All statistical tests will be two-sided. The required significance level of findings will be equal to or lower than 5%, nominal p-values will be presented. Where confidence limits are appropriate, the confidence level will be 95%.

Continuous variables will be summarized by a mean, standard deviation, minimum, median and maximum, and categorical variables by a count and percentage. For comparison of means (continuous variables), the two-sample t-test or the Wilcoxon rank sum test will be used as appropriate. For comparison of proportions (categorical variables), the Chi-squared test or Fisher's exact test will be used as appropriate.

If multiple measurements are taken in a single patient, statistics described below will be appropriately modified to accommodate the within patient correlation.

7.8.2 *Significance levels and handling of type I error*

7.8.2.1 *Type I Error*

The overall significance level for this study is 5% using two-tailed tests, except for treatment by site interaction that will be tested at a significance level of 10%.

7.8.2.2 *Hierarchy Approach for Secondary Endpoints Analysis*

The hierarchy approach will be adopted for the primary and secondary endpoints to control type I error due to multiple endpoint testing. Thus, the primary endpoint will first be analyzed and only if $p < 0.05$, will the secondary endpoints be analyzed.

7.8.3 *Demographic and Other Baseline Characteristics*

Demographic and baseline condition related characteristics will be tabulated and compared between the study groups by data type. Continuous variables will be summarized by a mean, standard deviation, minimum, median and maximum, and categorical variables by a count and percentage.

This data will include:

- Demographic data
- Medical history
- Migraine preventive medication
- Other concomitant medication
- Migraine attacks characteristics per ICHD-3 diagnostic criteria for migraine with and without aura
- Physical examination
- Laboratory (pregnancy) tests for women of childbearing potential

7.8.4 *Disposition of Patients*

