The numbers of patients who entered the study and completed each stage of the study will be provided per month, as well as the reasons for all post randomization discontinuations, grouped by major reason, e.g., lost to follow-up, adverse event, poor compliance, did not administer any treatment (with reasons). A list of discontinued patients, protocol deviations, and patients excluded from the performance analysis will be provided as well.

7.8.5 *Performance Analyses*

Primary Performance Analyses:

The primary endpoint is freedom from pain at 2 hours post treatment without rescue medications in at least 50% of treated attacks, a count and percentage of subjects free from pain will be calculated and presented for both study groups each with a two-sided 95% exact confidence interval. The groups will be compared with a chi-squared test.

If the null hypothesis is rejected in favor of the alternative hypothesis and the proportion (%) of subjects reporting freedom from pain at 2 hours post treatment without rescue medications in the treated group is greater than that of the sham group, the study will be deemed successful.

The primary endpoint will also be evaluated stratified by center using a Mantel-Haenszel test to assess the center by group interaction.

A sensitivity analysis of the primary end-point will be performed to assess the impact of missing data on the study outcome. This will be performed using several possible imputation methods.

Subset analysis:

Adjustment for other covariates such as demographics or other baseline patient characteristics may be performed by adding these variables into a logistic regression model.

Subgroup analysis according to use of preventive medications will be performed and reported by adding these variables to a logistic regression model.

Secondary performance analyses:

The secondary performance variables will be summarized by a count and percentage and compared with a chi-squared test.

Exploratory performance analyses:

A count and percentage of patients reporting freedom from pain (pain grade 0) 48 hours post treatment without rescue medications in at least 50% of treated attacks will be presented, the groups will be compared with a chi-squared test.

Use of rescue medications will be summarized by descriptive statistics per treatment group and compared between the groups with a t-test.

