7.8.7 Handling of Missing Data

A sensitivity analysis of the primary end-point will be performed to assess the impact of missing data on the study outcome using possible imputation methods for binary data. A “worse case” scenario analysis will be performed as well where subjects with missing data for the binary response assessment will be considered as a non-responder/ non-success.

Imputation of missing data may be performed on secondary and exploratory endpoints as well.

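### The handling of treated attacks with no 2-hour rating is not settled: 7.2.1 read literally scores them as failures, 7.4 and 7.8.7 imply otherwise, and the one spelled-out missing-data rule would not expose a sham–active gap in rating

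*Combined protocol and SAP*

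**What the plan says.** Section 7.2.1 gives the primary variable the value 1 under one condition, "the subject reports freedom from pain (pain grade 0) 2 hours post treatment without rescue medications in at least 50% of his/her treated attacks"; all other subjects get 0. The synopsis and 6.3.1 use the same denominator, treated attacks. None of these places says what happens to a treated attack for which no 2-hour rating was obtained.

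The main performance set is the mITT (7.7.2, 7.7.4). It requires one completed treatment and no rating. Only the per-protocol set (7.7.3), used as a sensitivity analysis, requires evaluable data on at least one qualifying attack.

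Section 7.4 plans the trial in evaluable subjects, meaning those who have data to analyse. Sections 7.8.5 and 7.8.7 promise sensitivity analyses by imputation methods that are not named. The one rule that is spelled out is a worst-case scenario in which "subjects with missing data for the binary response assessment will be considered as a non-responder".

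On the pilot, section 4.2 reports: "Complete reporting was obtained for 70% of activations for P200, P150, P100 programs, 58% of activations of P50 and 28% of placebo activations".

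**The concern.** Counting an unrated attack as a failure is conservative for the comparison only if both arms rate equally often. If sham subjects rate fewer attacks, the rule lowers the sham responder rate more than the active rate, and a difference appears with no treatment effect behind it. The pilot shows that such a gap can arise with this kind of sham. Program order was randomised within participant and blinded there, telephone follow-up was already in use, and the sham was again a very low-frequency pulse (0.1 Hz in the pilot, 0.1–0.5 Hz here, section 6.1).

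Two things are at stake. The first is the error rate of the single test on which success is declared. The second is pre-specification: with 7.2.1 pointing one way and 7.4 and 7.8.7 another, the rule for unrated attacks could be chosen after the pattern of missing ratings has been seen.

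**Working it through.** **1. The plan's own figure.** Section 7.4 takes 30% v 10%, and "with 80% power at a 5% level of significance will result in a total of 124 evaluable subjects". With pooled variance and no continuity correction:

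n per arm = [1.96·√(2·0.20·0.80) + 0.8416·√(0.30·0.70 + 0.10·0.90)]² / 0.20² = (1.1087 + 0.4610)² / 0.04 = 61.6, so 62 per arm and 124 in total. The figure reproduces.

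**2. The sections side by side.** Under the literal 7.2.1, every subject with a treated attack has a 0 or a 1, so the response is never missing in the mITT set. Under 7.4 a subject may lack data for analysis, and 7.8.7 provides for subjects whose binary response is missing. A separate worst-case analysis scoring them as non-responders would be redundant if 7.2.1 already did so. Both readings cannot be intended.

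**3. Does the worst-case rule protect?** Under the literal reading it changes nothing. Under the other reading it moves more sham than active subjects to non-response whenever sham has more missing ratings. In neither case does it test the assumption that matters.

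**4. Size under the literal reading.** From the plan: two-sided 5% ("The overall significance level for this study is 5% using two-tailed tests"), a chi-squared test ("The groups will be compared with a chi-squared test"), 62 per arm, up to four attacks. Assumed, not in the documents: exactly four treated attacks per subject, attacks independent, rating independent of outcome, and the same true per-attack pain-free rate p in both arms.

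With rating completeness c, the chance that an attack is both rated and pain-free is q = p·c. A subject is a responder with at least 2 of 4:

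R = 1 − (1 − q)⁴ − 4q(1 − q)³

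Two values of p are used: p = 0.1426, which gives R = 10% at full completeness (the planned sham rate), and p = 0.20, which gives R = 18%. The chance of a significant result for the device is the exact sum, over all pairs of responder counts, of the binomial probabilities where the pooled z exceeds 1.96. Nominal is 2.5%.

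| Completeness sham/active | p = 0.1426: measured R sham v active | Chance | p = 0.20: measured R sham v active | Chance |
|---|---|---|---|---|
| 90/90% | 8.3% v 8.3% | 2.5% | 15.1% v 15.1% | 2.3% |
| 80/90% | 6.7% v 8.3% | 5.1% | 12.3% v 15.1% | 6.3% |
| 70/90% | 5.2% v 8.3% | 9.5% | 9.7% v 15.1% | 14.2% |
| 28/70% (pilot) | 0.9% v 5.2% | 24.6% | 1.7% v 9.7% | 49.1% |

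Example, p = 0.20 with 80% completeness: q = 0.16, so R = 1 − 0.84⁴ − 4·0.16·0.84³ = 1 − 0.4979 − 0.3793 = 12.3%.

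**5. Sensitivity of the size.** At the maximum of 248 subjects, treated as a fixed size because the interim increase was not simulated, the three unequal rows become about 7%, 15% and 51% (p = 0.1426) and 9%, 25% and 81% (p = 0.20). Varying the true responder rate over 10–30%, the number of attacks over 1–4 and the within-subject correlation over 0–0.4 at N = 124 gives 4–8% for 80/90% and 16–77% for 28/70%.

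**The case against.** Several points on the other side are fair, and they limit the finding.

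- **The rule is not fixed.** A reader might infer that the plan definitely scores unrated attacks as failures and that the promised imputation has nothing to act on. The documents do not support that. Section 7.2.1 does not mention unrated attacks, and 7.4 and 7.8.7 point elsewhere. The imputation methods are unspecified, not excluded, and could be applied to attacks. The per-protocol analysis drops subjects with no evaluable attack. More detail may also sit in a stand-alone SAP, which section 9 lists as a separate document. What stands is the conflict and the missing rule.
- **The pilot gap is not a forecast.** A reader might carry the 28% v 70% straight into this trial. Complete reporting in the pilot covered four ratings per activation, and completeness of the 2-hour rating alone is not given. It was a crossover in which subjects could compare programs. This trial needs one 2-hour rating with medication use, in parallel arms, and adds automated alerts and EDC queries (6.4.4, 6.4.5). The last row of the table is therefore an upper scenario. Nor can one say that the true error must lie between the unequal rows, because equal completeness returns it to nominal.
- **The 20% per-attack rate is high.** It implies 18% responders, against 10% planned for sham. At the planned rate the pilot-gap figure is half as large.
- **Missingness may depend on outcome.** If unrated attacks are mostly not pain-free, scoring them as failures is close to correct and the bias is smaller. The documents do not settle this, which is why a sensitivity analysis is needed.

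**Conclusion.** The point holds in this form: the plan gives no consistent rule for a treated attack without a 2-hour rating. The literal rule favours the device if sham rates less, and the one stated missing-data analysis pushes the same way. Under the assumptions in the working, a 10-point completeness gap about doubles the one-sided error (5.1% at a true responder rate of 10%, 6.3% at 18%). A 20-point gap gives 9.5% or 14.2%, and the pilot's gap 24.6% or 49.1%. With equal completeness there is no inflation. These figures rest on four independent attacks, rating unrelated to outcome and no device effect. They show what a gap would do, not that one will occur. Severity: should fix, before any unblinded look.

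**What to change.** 1. In 7.2.1 and 7.8.7, state one rule for unrated attacks and for mITT subjects with no rated attack. Code an attack as a failure where rescue use within 2 hours is known, and otherwise as missing. The 48-hour form as listed in 6.4.2.3 asks whether rescue medication was taken but not when, so the source for its timing should be named.
2. Report 2-hour rating completeness by arm.
3. Add an attack-level sensitivity analysis that does not score missing as failure in both arms: multiple imputation of attack outcomes under a stated missing-at-random assumption, with a tipping-point analysis that varies the sham and active assumptions separately. Require the primary conclusion to be interpreted against it.
4. Fix before unblinding, including the interim look, whether imputation or unrated-as-failure is primary. Either is defensible if declared, and the choice is the sponsor's.

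Moving to a rated-attack denominator is not a full remedy. With few rated attacks per sham subject the 50% threshold behaves differently by arm: at 28/70% completeness with 62 evaluable per arm, the one-sided error ran from 0.3% to 10% for the device and 0.4% to 10% for sham.

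Cost: SAP wording and modest programming, with no new patients. Multiple imputation brings slightly more variance than single imputation.
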